## **Notes on Blood testing:**

- **Patients will be offered EMLA cream prior to blood being taken**
- **Approximately 2.5ml blood will be needed on each occasion.**
- **Blood will be taken by a qualified phlebotomist from the Princess Margaret Hospital haematology/biochemistry laboratory.**

---

## 7.3 Assessment of Pharmacokinetic Endpoints

**Not applicable.**

## 8 RATIONALE FOR STUDY

### 8.1 Rationale for study design

(Already discussed previously)

### 8.2 Rationale for Efficacy Assessments

**Bacterial Load:** Quantitative PCR (qPCR) is now well recognised as a sensitive and accurate quantitative measurement of bacterial load in standardised sputum specimens. Both [name] (TICHR/SPACH) and [name] (QIMR Brisbane) have validated this measurement in their laboratories. However, it is still not clearly established as to whether qPCR is superior to CFU and therefore we will be using both of these methods on all of our specimens. This will fortuitously allow us the opportunity of comparing qPCR results between two laboratories and qPCR against CFU which in itself will act as a valuable quality assurance exercise. Correlation between the tests will be analysed using the appropriate statistical method, such as Blandt-Altman plot. At this stage, it is planned to use the CFU results in the statistical analysis for the efficacy component of the study as it is probably still recognized as the “gold standard” for measurement of bacterial load.

**Biofilm measurements:** We are most fortunate that [name] laboratory is a leader in the use of confocal light microscopy imaging for the assessment and quantification of biofilm in sputum. In addition, [name] laboratory in Brisbane has developed and validated RNA probes for the assessment of the expression of genetic markers of biofilm production and virulence factors in *PsA* organisms. If our study is successful, these probes will show that the expression of these genetic markers for biofilm production will be significantly down regulated relative to the comparator.

## 9. ADVERSE EVENT DEFINITIONS AND REPORTING REQUIREMENTS

### 9.1 Adverse Events

#### 9.1.1 Definition of Adverse Events

**Per Note for Guidance on Good Clinical Practice (CPMP/ICH/135/95):**

**“An Adverse Event (AE) is any untoward medical occurrence in a patient or clinical investigation subject administered a pharmaceutical product and which does not necessarily have a causal relationship with this treatment. An AE can therefore be any unfavorable and unintended sign (including an abnormal laboratory finding), symptom or disease temporally associated with the use of a medicinal (investigational) product.**

**AE's include:**

- **Exacerbation or worsening of symptoms of a pre-existing medical condition or disease – in particular, cystic fibrosis.**

---

#### Confidentiality Statement

This document is confidential and is to be distributed for reference only to study staff, human research ethics committees and the applicable regulatory authorities. Information is not to be reproduced, abstracted or used for sharing of information for any purpose without with the written permission of the [name] or his delegate.

- 
- **Increase in frequency or intensity or a pre-existing episodic medical condition or disease.**
  - **Disease or medical condition that is newly diagnosed during the study, even though symptoms may have been present prior to participation in the study.**
  - **Overdose of investigational product or concomitant medication – whether this produces signs or symptoms, or not.**
  - **Events that the Investigator considers to be related to protocol-required procedures.**
  - **Abnormal assessments (including laboratory test abnormalities) that represent a clinically significant finding that was not present at baseline, worsened during the study, or led to discontinuation of investigational product.**

**Cystic Fibrosis symptoms that worsen during the study will be recorded as AE's.**

**AE's do not include:**

- **Medical or surgical procedures. The condition that leads to the procedure is the AE.**
- **Pre-existing medical condition or disease that does not worsen or increase in frequency.**
- **Situations in which an AE has not occurred (e.g. hospitalisation for social or convenience reasons).**
- **Changes resulting from normal growth and development (e.g. teething) that do not change significantly in severity or frequency from expected levels.**

#### **9.1.2 Reporting of Adverse Event Data**

**Participants will be interviewed in a non-directed manner to elicit potential AE's from the first dose of investigational product until the day 56 (follow-up) visit. A diary card will be provided to participants to record AE's experienced between clinic visits. The occurrence of an AE will be deduced from:**

- **history and physical examination at the time of clinic visits as per Clinic Visit Monitoring Sheet (attached to this protocol as an Addendum)**
- **Diary card**
- **CF Questionnaire**
- **Phone call visit assessments**
- **Any changes in the participant's physical examination, lung function, and/or signs and symptoms at any stage**

---

#### **Confidentiality Statement**

This document is confidential and is to be distributed for reference only to study staff, human research ethics committees and the applicable regulatory authorities. Information is not to be reproduced, abstracted or used for sharing of information for any purpose without with the written permission of the [name] or his delegate.

---

**AE's will be followed until resolution while the participant remains on the study. AE's that are considered to be related to investigational product will be followed until resolved or clinically stable.**

**All AE's will be recorded in the participant's Case Report Form (CRF).**

### **9.1.3 Intensity of Adverse Events**

**The Investigator will use the Common Terminology Criteria for Adverse Events (CTCAE) version 4.02 to grade the severity of AE's. The general clinical descriptions for each grade are as follows:**

**Grade 1 – Mild AE, transient and easily tolerated.**

**Grade 2 – Moderate AE, causes discomfort and interrupts participant's ADL**

**Grade 3 – Severe AE, causes considerable interferences with ADL, could be life-threatening or incapacitating.**

**Grade 4 – Life-threatening or disabling AE.**

**Grade 5 – Death related to AE**

### **9.1.4 Relationship to Investigational Product**

The relationship, or attribution, of an AE to the investigational product will be determined by the Investigator. The relationship of the AE to the investigational product will be coded according to the following definitions:

**Unrelated:** The adverse event is due to an underlying or concurrent illness or effect of another drug and is clearly not related to the investigational product (eg. has no temporal relationship to study drug or has a much more likely alternative aetiology).

**Unlikely:** The adverse event has little or no temporal relationship to the study drug and a more likely aetiology exists.

**Possibly:** The adverse event has a strong temporal relationship to study drug and an alternative aetiology is equally or less likely compared to the potential relationship to study drug.

**Probably:** The adverse event has a strong temporal relationship to study drug or recurs on re-challenge. Aetiology is unlikely or significantly less likely.

The Investigator should attempt to provide an alternative aetiology for all AE's considered to be unrelated, unlikely or possibly related to study drug. This will be recorded in the source documentation.

For the purposes of reporting to the relevant regulatory agencies, unrelated and unlikely AE's will be classified as Not Related, while Possibly and Probably related will be reported as Related.

## **9.2 Serious Adverse Events**

### **9.2.1 Definition of Serious Adverse Events**

---

#### **Confidentiality Statement**

This document is confidential and is to be distributed for reference only to study staff, human research ethics committees and the applicable regulatory authorities. Information is not to be reproduced, abstracted or used for sharing of information for any purpose without with the written permission of the [name] or his delegate.

---

A SAE or reaction is any untoward medical occurrence that results in one or more of the following:

- results in death
- is life-threatening
- requires inpatient hospitalization or results in prolongation of existing hospitalization
- results in persistent or significant disability/incapacity
- is a medically important event or reaction

Death is an outcome of an AE and not an AE in itself.

A “life threatening” event is any adverse therapy experience that, in the view of the Investigator, places the participant at immediate risk of death from the reaction as it occurred.

An “inpatient hospitalization” occurs when a participant is formally admitted to hospital for any length of time. It does not refer to Emergency Room or Accident & Emergency visits where the patient is observed and not admitted.

Medical and scientific judgment should be exercised in deciding whether other situations than those listed above should be considered serious. This may include important medical events that might not be immediately life-threatening or result in death or hospitalization but might jeopardize the participant or might require intervention to prevent one of the other outcomes listed above.

Regardless of the relationship of the event to the investigational product, the event must be reported as a SAE if it meets any of the definitions listed in this section.

#### **9.2.2 Reporting of Serious Adverse Events**

**SAE's will be reported from the time of informed consent until the Follow-up visit. All SAE's will be reported to the Human Research Ethics Committee (HREC) and Medical Monitor within 1 business day of site staff becoming aware of the event. The SAE Report Form will be completed and submitted with all information known at the time. A minimum of the SAE name, onset date and date of last dose of investigational product should be provided, and if possible, the form should be reviewed and signed by an Investigator prior to submission.**

#### **9.2.3 Follow up of Serious Adverse Events**

If site staff becomes aware of new information regarding an SAE, a follow-up report should be completed and forwarded to the HREC within 5 days. New information may include the acquisition of relevant hospital records, reports and/or laboratory results.

SAE's that are ongoing at the end of the study should be followed up until a final assessment is possible, and until all queries have been resolved.

#### **9.2.4 Reporting to Regulatory Authorities**

It is important that all known information at the time of the SAE is reported to the Medical Monitor within the protocol-required time frame, as expedited reporting to the appropriate regulatory authorities may be required based on the following criteria:

---

## No Reporting

This requirement applies if the SAE is deemed not serious by the Medical Monitor.

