## Expedited Reporting

This requirement applies if the SAE is classified as serious, unexpected and related to the investigational product. During these circumstances, the appropriate health authorities must be informed within 15 days, however fatal or life-threatening events must be reported within 7 days.

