### Confidentiality Statement

This document is confidential and is to be distributed for reference only to study staff, human research ethics committees and the applicable regulatory authorities. Information is not to be reproduced, abstracted or used for sharing of information for any purpose without with the written permission of the [name] or his delegate.

All reported AE's will be coded using the CTCAE and grouped by body system. The incidence of AE's in each treatment arm will be tabulated by seriousness, severity and relationship to investigational product. If an AE is reported more than once during the study for a given participant the greatest severity and worst-case relationship will be reported in the tables. AE's will also be listed for individual participants. AE's which lead to withdrawal from the study will be listed and summarised per treatment arm. A separate tabulation and listing of SAE's will be provided.

Concomitant medication use will be summarised descriptively using frequency and percentage of participants by treatment arm.

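### Section 9.2.4 exempts an SAE from regulatory reporting on the Medical Monitor's opinion that it is not serious, without tying that opinion to the seriousness criteria of section 9.2.1

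*Protocol*

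**What the plan says.** **Definition (Protocol section 9.2.1).** Seriousness follows from a list: death, a threat to life, admission or prolonged admission, lasting or significant disability, or a medically important event. Whatever the cause, "the event must be reported as a SAE if it meets any of the definitions listed in this section". A life-threatening event is one that, "in the view of the Investigator, places the participant at immediate risk of death from the reaction as it occurred". Room for judgement is described in these terms: "Medical and scientific judgment should be exercised in deciding whether other situations than those listed above should be considered serious".

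**Site reporting (section 9.2.2).** "All SAE's will be reported to the Human Research Ethics Committee (HREC) and Medical Monitor within 1 business day of site staff becoming aware". No exception is given.

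**Onward reporting (section 9.2.4).** The section explains that "expedited reporting to the appropriate regulatory authorities may be required based on the following criteria", and then sets out three classes.
- No Reporting: "This requirement applies if the SAE is deemed not serious by the Medical Monitor".
- Standard Reporting: serious events that are expected and related, expected and not related, or unexpected and not related.
- Expedited Reporting: "This requirement applies if the SAE is classified as serious, unexpected and related to the investigational product". The limit is 15 days, or 7 days for fatal or life-threatening events.

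**Analysis (section 10.1.3).** AEs are tabulated by seriousness, severity and relationship, and "A separate tabulation and listing of SAE's will be provided".

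**The concern.** Under section 9.2.1 an SAE is serious by definition. A class for SAEs that are deemed not serious therefore sits badly with that section. The wording does not confine the class to events submitted as SAEs by mistake, and it reaches events that do meet a criterion.

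Two people are also given the same question without a rule for when they differ. Section 9.2.1 rests the life-threatening criterion on the Investigator's view, while section 9.2.4 lets the Medical Monitor's view decide whether the event goes to the regulator at all.

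At stake is whether the regulator hears of a serious, unexpected and related event in a trial of a nebulised combination in children from 6 years of age. Expedited reporting exists for exactly that kind of event.

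**Working it through.** There is no figure to reproduce. The check sets sections 9.2.1 to 9.2.4 side by side and follows one event through them.

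1. **Are the reporting classes complete for serious events?** Section 9.2.4 uses two further attributes: expected or unexpected, and related or not related. That gives 2 × 2 = 4 combinations. Standard Reporting covers three and Expedited Reporting covers the fourth, so 3 + 1 = 4. Every serious event has a reporting class, and none of the four combinations leads to No Reporting.

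2. **How can an event reach No Reporting?** Only through the seriousness decision, since all four combinations start from a serious classification. That decision is the single gate in front of both regulatory routes.

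3. **What governs the gate?** For the site it is the list in 9.2.1, with the Investigator's view deciding what is life-threatening. For the regulator it is the Medical Monitor's opinion. The No Reporting text does not refer to the 9.2.1 list, does not ask for the Investigator's agreement, does not require a record and does not say whose view prevails.

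4. **An event followed through.** Take an event that prolongs the hospital stay and that is judged unexpected and related.

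| Step | Section | Result |
|---|---|---|
| Meets a listed criterion | 9.2.1 | It is an SAE and must be reported as one |
| Site reports it | 9.2.2 | HREC and Medical Monitor informed within 1 business day |
| Classed as serious | 9.2.4, Expedited | Regulator informed within 15 days |
| Deemed not serious by the Medical Monitor | 9.2.4, No Reporting | Regulator not informed |

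The last two rows concern the same event. The only difference between them is one opinion, and the protocol states no standard for it.

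5. **What does the opinion leave untouched?** The site's report under 9.2.2 has already gone out and is not withdrawn. Follow-up information still goes to the HREC under 9.2.3. The AE stays in the CRF under 9.1.2 and is listed and tabulated under 10.1.3. The gap is confined to onward reporting to regulators.

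**The case against.** The strongest reply is that the sections impose different duties with different recipients. Sections 9.2.1 and 9.2.2 tell the site what to send to the HREC and the Medical Monitor, and section 9.2.4 tells the Medical Monitor what to pass on. Both can be followed for the same event, so 9.2.4 does not cancel the 9.2.1 duty. This stands, and it limits the point to the regulatory route.

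A second reply is that the class may be meant to screen out reports that meet no criterion. Some criteria, such as medically important, need judgement in any case. That is a plausible purpose, but the text does not state it, and the wording reaches further.

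Third, there are safeguards. The medical monitor is blinded (section 3.9), so an event cannot be downgraded by treatment arm, and an independent DSMC oversees safety (section 11). These reduce the risk of a distorted comparison. They do not put the event before the regulator. Section 9.2.2 names only the HREC and the Medical Monitor as recipients of SAE reports, and the DSMC charter is not at hand.

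Three stronger readings are tempting and are not supported:
- A reader might infer that downgraded events vanish from the SAE table, and that with 16 children per arm each one would move that arm's incidence by 1/16 = 6.25 percentage points. Nothing in section 10.1.3 links the table to the Medical Monitor's classification. Which classification feeds the table is also a detail that a statistical analysis plan may settle.
- A reader might infer that re-admissions would be dismissed as ordinary cystic fibrosis. That is a judgement of cause, which section 9.1.4 gives to the Investigator. It bears on relatedness and not on seriousness.
- A reader might infer that the Medical Monitor can only downgrade. No sentence prevents the Medical Monitor from treating an event as serious.

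**Conclusion.** The concern holds in a limited form. Section 9.2.4 states a rule that, as written, lets one opinion remove an event meeting a 9.2.1 criterion from both Standard and Expedited reporting. It neither ties that opinion to the criteria nor says how a disagreement with the Investigator is resolved. This is a defect in a stated rule, and not a detail left for the statistical analysis plan.

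The size cannot be put in numbers. The protocol gives no SAE rates and no indication of how often the two views would differ. There is no effect on sample size, power or the efficacy analysis, and none is shown on the SAE table.

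The conclusion assumes that the No Reporting text is applied literally. If it is applied only to events that meet no 9.2.1 criterion, practice is sound and only the wording needs correction. The change is worth making because it costs little and protects the reporting of serious, unexpected and related events.

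**What to change.** Amend the No Reporting paragraph of section 9.2.4 in one or two sentences:
- No Reporting applies only to an event that, on review, meets none of the criteria in section 9.2.1.
- Where the Investigator and the Medical Monitor disagree on seriousness, the event is treated as serious for regulatory reporting, and the disagreement is recorded in the SAE report.

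No change to section 9.2.2 or section 10.1.3 is needed for this point. The cost is a short protocol amendment and possibly a few extra reports to the regulator. Their number cannot be estimated from the protocol.

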## Standard Reporting

This requirement applies if the SAE is classified as any of the following:

Serious, expected, and related to the investigational product

Serious, expected and *not* related to the investigational product

Serious, *unexpected* and *not* related to the investigational product

## Expedited Reporting

This requirement applies if the SAE is classified as serious, unexpected and related to the investigational product. During these circumstances, the appropriate health authorities must be informed within 15 days, however fatal or life-threatening events must be reported within 7 days.

## 10. STATISTICAL ANALYSIS

### 10.1 Statistical Methods

#### 10.1.1 Demographic data

Demographic data will be displayed and summary statistics will be used to describe the study populations.

#### 10.1.2 Efficacy

All efficacy analysis will be performed using the modified Intent to Treat (mITT) population, which is defined as all randomised participants who received at least one dose of investigational product. Selected efficacy analyses will be repeated in the per-protocol population, which is defined as participants having completed  $\geq 75\%$  of doses with not more than 3 consecutive missed doses.

As this is a pilot/proof of concept study, the results will in the first instance be used afterwards to assess the standard deviation of the within-subject variations. If this is similar to previous studies, we expect a sample size of 32 patients will have an 80% power at one standard deviation to detect a difference of  $2.6 \log^{10}$  CFU per gram in the primary efficacy endpoint between treatment groups after 6 weeks at the 0.05 level of significance. If however, the standard deviation is higher than in previous studies, the methodology in any further follow-up studies will have to be reviewed in the light of this. On the other hand, if the standard deviation is lower than in previous studies, this will lend more power to the statistical significance.

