**Confidentiality Statement**

This document is confidential and is to be distributed for reference only to study staff, human research ethics committees and the applicable regulatory authorities. Information is not to be reproduced, abstracted or used for sharing of information for any purpose without with the written permission of the [name] or his delegate.

	patient or quality of the data
RANDOMISATION	1:1 investigational product to comparator
INVESTIGATIONAL PRODUCT	
 
• Calcium disodium ethylenediamene tetra acetate (Ca-EDTA) will be supplied as a sterile TRIS-buffered solution in a single-use syringe.
 
• 1.5ml Ca-EDTA solution will be added to 2.5ml Tobramycin solution (Tobra-Day®) and administered via a nebuliser
 
• Final concentration: 50mMol
 
• Dose: 75mg Ca-EDTA
 

REFERENCE THERAPY	
 
• Placebo will be supplied as a sterile Tris-buffered saline solution in a single-use syringe.
 
• 1.5ml placebo solution will be added to 2.5ml Tobramycin solution (Tobra-Day®) to form the comparator, and administered via a nebuliser.
 

DURATION OF TREATMENT	6 weeks (42 days) – 14 days in conjunction with intravenous antibiotics followed by 28 days as outpatient treatment
STUDY DESIGN	See Table of Assessments below
EFFICACY CRITERIA	
Relative to comparator:
 
Primary
 
 
1. Greater reduction in bacterial load
 
 
Secondary
 
 
2. Greater reduction in biofilm mass
 
3. Reduced capacity for PsA to produce biofilm
 
 
Exploratory
 
 
4. Greater reduction in MIC of PsA to Tobramycin and other antibiotics
 
5. Greater clinical improvement (questionnaire and FEV1)
 
6. Greater reduction in evidence of inflammation
 
7. Reduction in beta-lactamase production by PsA
 
8. Differences in lung microbiome
 

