**Confidentiality Statement**

This document is confidential and is to be distributed for reference only to study staff, human research ethics committees and the applicable regulatory authorities. Information is not to be reproduced, abstracted or used for sharing of information for any purpose without with the written permission of the [name] or his delegate.

	
 
The first aim would be to establish the standard deviation of within-subject variations. If this standard deviation proves to be similar to previous studies, 32 patients (16 in each group) study will have an 80% power of detecting a difference in the primary efficacy endpoint to the 0.05 level of significance. If not similar, the standard deviation found in our population will guide us as to required numbers for future Phase III studies to demonstrate efficacy.
 
 
Safety:
 
 
Acute changes in respiratory and systemic symptoms and signs, PFTs, and blood parameters will be summarised, with categorical analysis of clinically significant findings.          All reported AE's will be coded and grouped by body system. AE's will be tabulated by treatment group and sorted by body system. The incidence of AE's in each treatment group will be tabulated by seriousness, severity and relationship to investigational product.
 
Concomitant medication use will be summarised.
 

TRIAL SITE	Princess Margaret Hospital for Children

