### **3.7.3 Replacement of Participants**

**Participants who prematurely discontinue from the study for any reason will not be replaced.**

## **3.8 Investigational Product Accountability and Disposition of Clinical Study Supplies**

**During the 2-week inpatient phase, an accountability log will be attached to each individual trial patient's medication chart with full explanation and documentation to nursing staff on administration and recording of trial drug. Should the patient be discharged on "Home IV", he/she will be given the remainder of the 2-week inpatient trial drug with full explanation of how it should be administered. At the 2-week review visit, the patient will be required to return all used and unused trial drug items, when pharmacy will perform a standard accountability log, before dispensing the 4-week outpatient batch of trial drug. At the 6-week review visit (4 weeks after cessation of IV antibiotic treatment)) the patient will again be requested to return all used and unused items for standard pharmacy accountability logging. A spare 3-day reserve supply will be issued to each patient to be kept separate from the main batch for use if the main batch is mislaid or damaged. Pharmacy will arrange appropriate**

---

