#### **10.1.4 Data Handling Conventions**

In general, values for missing data will not be imputed unless specified. Details of missing data conventions will be provided in the statistical analysis plan.

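### The 80% power is conditioned on an undefined within-subject SD, although the parallel-group comparison needs the between-patient SD, and it leaves no margin for any loss from the 32 patients

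*Protocol*

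**What the plan says.** The synopsis (Statistical Methodology) opens its efficacy paragraph with the pilot's purpose: "The first aim would be to establish the standard deviation of within-subject variations". If that SD resembles earlier studies, "32 patients (16 in each group) study will have an 80% power" for the primary endpoint. If it does not, the SD found in the trial is to guide the numbers for Phase III.

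Section 10.1.2 repeats the condition and adds the effect size, 2.6 log10 CFU per gram. It reads "we expect a sample size of 32 patients will have an 80% power at one standard deviation to detect a difference of" that amount. The comparison is made "between treatment groups after 6 weeks at the 0.05 level of significance". Allocation is "1:1 investigational product to comparator".

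Neither place gives the SD a separate numerical value, says which quantity it describes, or allows for patients without an evaluable result. On losses:
- Section 3.7.3 says "Participants who prematurely discontinue from the study for any reason will not be replaced".
- Section 10.1.4 says "values for missing data will not be imputed unless specified" and leaves the detail to the SAP.
- Section 7.1 substitutes a nasopharyngeal swab when induced sputum cannot be obtained, and accepts that this may limit some tests.
- Section 7.2 provides for withdrawal from the study after a post-dose FEV1 fall judged related to the drug.

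**The concern.** The primary endpoint (section 3.2.1) is a greater reduction in bacterial load than in the comparator arm, in a parallel-group trial. The precision of that comparison depends on how much patients in the same arm differ from one another in the analysed quantity. A within-subject SD, in ordinary usage, is the spread of repeat measurements in one patient. It is a different quantity, and it is smaller than the SD of a change built from two such measurements.

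Two things are at stake. The first is the stated power, which a reader will use to judge a null result. The second is the SD itself. Estimating it is the pilot's declared first aim, and it is meant to inform Phase III. A statistician who takes the label literally would estimate a different SD from the one a parallel-group sample size needs. Separately, the 80% uses every one of the 32 patients, while the protocol describes several ways in which a patient may have no usable 6-week CFU value.

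**Working it through.** **Inputs from the protocol.** 32 patients, 16 per arm, 1:1 (synopsis). Difference 2.6 log10 CFU/g, described as one standard deviation; level 0.05; power 80% (section 10.1.2). Sidedness is not stated. One SD equal to 2.6 gives a standardised difference d = 2.6/2.6 = 1.0.

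**Step 1: reproduce the stated figure.** For two independent groups, two-sided, power ≈ Φ(d·√(n/2) − 1.96).
- n = 16, d = 1: Φ(2.83 − 1.96) = 80.7%.
- The same comparison by two-sample t-test gives 78.1%; 80% would need 17 per arm, 34 in total.
- Other readings do not give 80%. One-sided 0.05 gives 88.2%. An SD of 1 with a difference of 2.6 gives over 99.9%, as does a paired test on 32.

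So the figure comes from the correct parallel-group formula. It requires the between-patient SD of the analysed quantity to be 2.6 and all 32 patients to be evaluable.

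**Step 2: loss, keeping SD = 2.6.** The protocol gives no loss rate, so the evaluable numbers below 16 are assumptions.

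| Evaluable per arm | Normal approximation | t-test |
|---|---|---|
| 16 | 80.7% | 78.1% |
| 15 | 78.2% | 75.3% |
| 14 | 75.4% | 72.1% |
| 13 | 72.2% | 68.7% |

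One lost patient per arm is enough to bring even the normal approximation below 80%.

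**Step 3: if 2.6 is a repeat-measurement SD (assumption).** A change is the difference of two measurements, so its SD is at least 2.6 × √2 = 3.68, and d = 2.6/3.68 = 0.707.
- Power with 16 per arm: Φ(0.707 × √8 − 1.96) = Φ(0.04) = 51.6%; by t-test 49.0%.
- 80% power needs 32 per arm by normal approximation, 64 in total.
- Sample size scales with SD², so sizing on 2.6 instead of 3.68 gives (2.6/3.68)² = 1/2 of the number needed for a change analysis.
- With baseline adjustment the residual SD is 2.6 × √(1 + ICC). At assumed intraclass correlations of 0.3, 0.5 and 0.7 this is 2.96, 3.18 and 3.39, with t-test power of 67%, 61% and 56%.

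**Step 4: what baseline adjustment offers if 2.6 is the SD of the change.** The ratio of residual SD to change SD is √((1 + ρ)/2). At an assumed pre/post correlation ρ = 0.5 it is 0.866, so d = 1/0.866 = 1.155. Power is 88% with 16 per arm and 84% with 14.

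**Step 5: precision of the SD the pilot will estimate.** With all 32 evaluable there are 30 degrees of freedom. The 95% limits are the estimate multiplied by √(30/χ²), that is 0.80 to 1.34.

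**The case against.** The strongest reply is that the arithmetic is right. It uses the parallel-group formula, it reproduces, and the gap between 80.7% and 78.1% is only the choice of approximation. The endpoint is a within-patient reduction compared between arms, so within-subject variations may simply be loose wording for the spread of patients' changes. On that reading, the power input and the Phase III input are both appropriate apart from losses. This stands. A reader might infer that the design definitely lacks 80% power, or that the SD passed to Phase III is definitely the wrong one. The documents support neither, because they never define the SD and the earlier studies are not available to settle it.

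The losses are also assumed. Section 3.6 encourages patients who stop the product to keep attending visits, section 7.1 uses induced sputum with fallbacks, and missing-data conventions are deferred to the SAP. So 13 or 14 per arm is a scenario, not a forecast. What remains is that the stated figure has no margin for any loss.

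Finally, section 10.1.2 calls the trial a pilot, makes the power conditional and says that methodology will be reviewed if the SD is higher. That lowers the weight of the power claim. It does not help with the label, because that same SD is the one to be reviewed and carried forward.

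**Conclusion.** The point holds as a mislabelled or undefined SD and a power figure with no allowance for loss. The 80% is right (78–81%, depending on approximation) if 2.6 log10 CFU/g is the pooled within-arm SD of the 6-week change and all 32 patients are evaluable. Under that reading, t-test power falls to 75%, 72% or 69% with an assumed 15, 14 or 13 evaluable per arm.

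The larger figures, about 49–52% power and a Phase III trial of about half the size needed, apply only if 2.6 is the repeat-measurement SD of a single sample and the analysis is an unadjusted change. They show why the definition matters; they are not an established property of this trial. Given the pilot status and the conditional wording, this should be corrected but is below must-fix.

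**What to change.** - In section 10.1.2 and the synopsis, state which SD the 2.6 is. If it is the pooled within-arm SD of the 6-week change in log10 CFU/g, say so, and restate power as about 78–80% with all 32 evaluable, with the lower figure at the expected evaluable number. If it is a repeat-measurement SD, recompute the power.
- Replace the within-subject SD as the pilot's target with the pooled within-arm SD of the 6-week change, or the baseline-adjusted residual SD. Report it with its confidence limits as the input to Phase III.
- Consider adjusting the primary comparison for baseline log10 CFU/g. A pre-treatment sputum sample is already planned. Under the assumptions of Step 4, this more than offsets the loss of two patients per arm.

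The cost is protocol wording and a slightly less favourable stated power. If 2.6 proves to be the SD of the change, no extra patients or samples are needed. If it proves to be a repeat-measurement SD, the restated power will be materially lower, and the sponsor can then present the trial on the precision it offers.
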